## Study 15-1052 Investigator Timetable and Procedures-Aim 1b

IRB #: 15-1052  
Project Title: Reprometabolic Syndrome Mediates Subfertility in Obesity  
Principal Investigator: [name]

## **Description, Risks and Justification of Procedures with Data Collection Tools**

### **Risks and plan to minimize risks:**

***Risks of a high fat diet:*** it is expected that a 48% energy from fat diet administered for an entire menstrual cycle will not pose a significant risk to participants, as this is within the range of dietary fat consumption among the US population (90th centile; 36). However, we will monitor all participants through 2 recovery cycles to determine whether or not the hormonal deficits associated with obesity are induced and then recover when the diet is withdrawn. While long term consumption of diets that are high in fat have been associated with development of coronary artery disease, these data are by no means well established for women and often relate to the particular type of fat consumed (polyunsaturated versus saturated fat). Reduction in fat consumption for a mean of 8.1 years in the Women's Health Initiative was not associated with reduced cardiovascular disease . Moreover, a recent study of gestational diabetics administered a diet high in complex carbohydrates and fat (45% calories from fat) for an entire trimester of pregnancy, did not result in any adverse, short-term metabolic outcomes. It therefore seems exceedingly unlikely that an intervention of this degree and duration will have any kind of negative impact. We will monitor reproductive hormones and lipid panels throughout and will repeat these and routine safety labs at the end of the recovery cycle.

### ***Risks of medications to be administered:***

***Insulin:*** recombinant human insulin (Humulin) will be administered. Its chief side effect is hypoglycemia. As all participants will be undergoing glucose monitoring every 5 minutes during the clamp studies, their glucose level will be continuously adjusted by adjusting the intravenous dextrose to maintain blood glucose within a 90-100 mg/dl range.

***Intralipid (Aim 1A only):*** Intralipid will be administered as an intravenous infusion. Side effects reported for this compound include headache, dizziness, nausea, vomiting, sweating, difficult or labored breathing, or, rarely, anaphylactic type reactions have been reported. Participants will be monitored throughout the infusion in the CTRC, where epinephrine is readily available for any allergic reaction.

***Dextrose (20%):*** will be administered to maintain the blood glucose level between 90-110 mg/dl.

***Heparin:*** will be used in concert with the intralipid infusion to maintain catheter patency and stimulate lipolysis. Adverse reactions to high doses of heparin include hemorrhage and thrombocytopenia. Very long term use (months) has been associated with osteopenia. Heparin will be used at very low doses in this experiment and may induce short term anticoagulation but would not be expected to cause thrombocytopenia or osteopenia at this low dose.

IRB #:

15-1052

Project Title:

Reprometabolic Syndrome Mediates Subfertility in Obesity

Principal Investigator: [name]

Anaphylactic reactions have been reported to occur with heparin, and participants will all be given heparin at the CTRC where nursing personnel monitor them continuously and epinephrine is readily available. In addition:

- 1) aPTT will be confirmed before participants leave the CTRC to ensure levels are not in excess of the targeted degree of therapeutic anticoagulation in the outpatient setting (aPTT < 120 seconds -- the upper target of therapeutic anticoagulation used in inpatient or outpatient setting).
- 2) aPTT will be measured during peak infusion (mid-interval) at ~3 hours. The heparin infusion rate will be reduced by 50% if aPTT is > 100, and by 25% (to standard anticoagulation dosing) if the aPTT is 80-100. Levels will be re-measured at 6 hours (toward the end of the infusion) to ensure the aPTT is < 120 secs before allowing the participant to be discharged. If the 6 hour aPTT is > 120, another will be checked at 7 hours, one hour after discontinuation of the heparin (t=7 hours) to ensure that the aPTT is < 120 prior to discharge or on a downward trajectory that ensures aPTT<120 by time of discharge.
- 3) Patients will be counseled about possible side effects of longer clotting times, behaviors to avoid in the coming hours, what to look for and what steps to take should symptoms develop. Aspirin and Ibuprofen should be avoided for at least 2 hours if the patient is discharged with an abnormal aPTT (>35 seconds).

**GnRH (gonadotropin releasing hormone):** GnRH is a 10 amino acid peptide that has a short serum half-life and minimal known antigenicity. If given in large doses, it has been associated with a risk of multiple pregnancy. Our participants will all be using contraception and tested for pregnancy at the onset of each assessment.

*Iron Supplements:* Common side effects include an upset stomach, pain, constipation or diarrhea, nausea, or vomiting.

**Risks to pregnant women:** Although none of the medications listed above are contraindicated in pregnant women, there is no reason for a pregnant woman to be exposed to any of the potential risks above. Our goal is to study how obesity and a high fat diet might mediate abnormal reproduction in women, and pregnant women are not eligible for these studies. To avoid any possible exposure, participants will be included only if they are using a reliable non-hormonal method of contraception and they or their partner has been sterilized. They will only undergo frequent sampling studies in the early follicular phase of the menstrual cycle, and thus are extremely unlikely to be pregnant with a normal gestation if they have just had a menstrual period. As a further safeguard, we will verify the menstrual history with the participant before each frequent sampling study and perform a high-sensitivity urine pregnancy test (40 mIU/ml of hCG) prior to beginning any of the blood sampling sessions.

**IRB #:** 15-1052  
**Project Title:** Reprometabolic Syndrome Mediates Subfertility in Obesity  
**Principal Investigator:** [name]

**Risks of frequent blood sampling:** This procedure is commonly associated with bruising and bleeding at the site of the IV line. Rarely, anemia can result if amounts of blood withdrawn are excessive. Participants will participate in 6 hour frequent blood sampling sessions. During these sessions an IV will be placed in a vein in their arm and small amounts of blood (a little less than 1 teaspoon) will be drawn approximately every ten minutes (less than 1 cup total over 6 hours, or approximately 1.2 full cups of blood to be drawn in the total of two, 6-hour sessions).

A CBC will be taken at the end of the gonadotropin pulsatility study to assure that the participant has not become anemic. Screening and safety lab tests are likely to require another 20cc and safety labs at the end of the study will require a further 20cc. The total amount of blood over approximately 12 weeks is within permissible guidelines. As is our practice, we pre-screen all participants for an adequate hemoglobin level prior to entry (11gm/dl or greater), and supplement with iron (325mg daily for 3 months). VAMP tubing will be used when a nurse is available. Gravity tubing will be used if a nurse is unavailable and the lab technician must perform the frequent sampling for visits 1.1 and 6.1. By using gravity tubing, there will be an additional 18 milliliters of blood taken per 6-hour frequent sampling visit (1.1, and 6.1). There will still be less than 2/3 cup of blood taken per visit, as stated in the consent form.

**Infiltration:** There is also a risk of infiltration, or blood backing up in the IV line and leaking into the surrounding tissue, which can cause bruising and/or discomfort.

**Risk of DEXA:** DEXA is a way of looking inside the body by using X-rays. X-rays are a type of radiation. Your natural environment has some radiation in it. A DEXA will give the participant about the same amount of radiation that they would get from the environment in 4 days.

**Risk of muscle oxygenation:** This is a non-invasive test with no significant risk or discomfort.

**Risk of Loss of Confidentiality/Privacy:** There is a risk that people outside of the research team will see the participant's research information. Through operating in accordance with university standards and in compliance with HIPAA, we will do all that we can to protect their information, but it cannot be guaranteed.

Data will be stored in OnCore, which limits access to PHI through usernames, passwords, and access levels. Data may also be stored in Excel on an encrypted drive that will be password protected with access restricted to study personnel only and institutional or federal officials as required by institutional regulations or law. The shared drive is backed up every evening. Specimens are stored in a locked refrigerator or freezer in the PI's laboratory, which is in turn restricted in access to outside individuals based on access badging. Specimens and data are stored coded with an alphanumeric participant identification code. This code is not linked to any identifiable data about the participant. The file that links identifying information to study ID is double password protected in a separate folder and kept apart from primary research specimen data.

**IRB #:** 15-1052  
**Project Title:** Reprometabolic Syndrome Mediates Subfertility in Obesity  
**Principal Investigator:** [name]

**Data and Safety Monitoring Plan:** This proposal involves substantial participant commitment and requires adequate recruitment of participants to be successful. Multiple medications and procedures will be administered to study participants. [name] and [name], have agreed to serve as safety officers for this study. The safety officers will be provided with monthly recruitment updates and will be provided with any adverse event reports as they are submitted to the IRB. An initial meeting with the Safety Officer will be held before any subject enrollment in the study occurs in order for the Safety Officer and study team to establish a meeting schedule, review the study protocol, and study/participant termination guidelines. The Safety Officer will meet after the first 5 participants have been enrolled, and then after the enrollment of every 10 additional participants. They will assist the PI by making recommendations designed to improve recruitment or enhance the safety of the study for all participants. This is not a clinical trial and none of the information generated by the study will be used to promote drug marketing for any of the agents that are used.

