***Aim 2:***

**IRB #:** 15-1052  
**Project Title:** Reprometabolic Syndrome Mediates Subfertility in Obesity  
**Principal Investigator:** [name]

We will determine the metabolic consequences of the induction of the reprometabolic phenotype with HFD(Aim 1b) by assessing the glucoregulatory and anti-lipolytic actions of insulin with a 2-stage, hyperinsulinemic, euglycemic clamp (HEC) to evaluate both suppression of lipolysis (low dose: 4 mU/m^2/min) and suppression of hepatic glucose production (40 mU/m^2/min).

**Aim 2 Primary outcome:** Our primary outcome will be M, which represents the steady state amount of glucose metabolized at the set insulin infusion rate under euglycemic conditions, which is equal to the glucose infused when the participant is euglycemic during the second stage of the HEC. The final 30 minutes of the clamp period will be considered steady state. Glucose concentrations will be determined with the glucose oxidase method (Beckman Glucose Analyzer 2; Beckman Instruments, Fullerton, CA), while ELISA methods will be used for insulin measurements (Alpco, Salem, NH).

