#### Data Summary for our 6 in-patient visits (4 clamps, 2 FSS-only)

**Visit 1.2:** After the 1.1 visit, the participants will return after fasting overnight. They will have their height and weight recorded. They will provide a blood sample for baseline safety labs (CBC/CMP, lipid panel, FFAs). Additional blood samples are drawn during the basal period, and Stages 1 and 2 of the HEC to assess insulin, FFAs and glycerol. Participants will have 2 IV lines placed in their arm for infusion of insulin (constant) and 20% dextrose (variable, as needed to maintain euglycemia, defined as a blood glucose of 90-110 mg/dl) and glucose monitoring. A HEC will be performed for 3 hours (180 minutes). Plasma glucose is measured every 5 minutes, with concentrations determined immediately upon collection, and the glucose infusion rate adjusted to maintain euglycemia throughout the HEC. At the end of the visit they will provide another blood sample for safety labs and will be provided with lunch.

IRB #: 15-1052

Project Title: Reprometabolic Syndrome Mediates Subfertility in Obesity

Principal Investigator: [name]

Participants will be provided a three month supply of iron supplements and be instructed to take one 325mg tablet daily for the next three months.

## Cycle 2

With the onset of the next menstrual period (Menses #2, start of Cycle #2), a eucaloric, high fat diet (48% energy from fat) will be administered. Participants will continue collection of daily morning first urine, use their Fitbit, and intake of iron supplements over the course of Cycle 2. Also, participants will be asked to use home ovulation predictor kits.

**Visits 2-5:** Participants will be asked to pick up meals twice per week, return their empty food containers, and will be asked if they have any questions about the diet. At the first meal pick-up each week, they will also have their weight recorded, and they will provide a fasted blood sample for fatty acid analysis. At each of these visits, they will return their collected urine and receive more urine collection supplies. The study team will either review the fitbit information and go over questions about the diet in person or via a phone, zoom, or skype call. In addition to the aforementioned supplies we will also provide each participant with a second fecal collection kit to obtain a post-diet fecal sample.

## Cycle 3

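### The upper limit of the clamp glucose target is 110 mg/dl in two places and 100 mg/dl in a third, and M is not corrected for glucose drift in the steady-state window

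*Combined protocol and SAP*

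**What the plan says.** Three places in the protocol give a glucose range for the clamps.

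- **Aim 1B, Cycle 1, Visit 1.2 (the clamp procedure):** the dextrose infusion is varied to hold "euglycemia, defined as a blood glucose of 90-110 mg/dl". This is the only place that formally defines euglycemia.
- **Risks of medications to be administered, Dextrose:** dextrose "will be administered to maintain the blood glucose level between 90-110 mg/dl".
- **Risks of medications to be administered, Insulin:** dextrose is adjusted to "maintain blood glucose within a 90-100 mg/dl range". The sentence opens "As all participants will be undergoing glucose monitoring every 5 minutes during the clamp studies", so it is not confined to one aim.

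The Aim 2 outcome section depends on this condition. It states: "Our primary outcome will be M, which represents the steady state amount of glucose metabolized at the set insulin infusion rate under euglycemic conditions". It equates M with the glucose infused during the second clamp stage while the participant is euglycemic, and gives no numerical range. It adds: "The final 30 minutes of the clamp period will be considered steady state". It sets no stability criterion for that window, and no correction for the glucose level held or for a change in it.

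The post-diet clamp (Visit 6.2) is described as a repeat of Visit 1.2.

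**The concern.** M is read from the glucose infusion rate needed to hold a target, so the target is part of the measurement. With two upper limits written down, one operator may leave a reading of 105 mg/dl alone and another may cut the infusion. An analyst asked whether the final 30 minutes were euglycemic could also answer either way.

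At stake is the precision of the Aim 2 primary paired comparison. The Data Analysis Plan sets 15 women for that aim by analogy with studies of 12, and says that no preliminary data on M were available. With so few women and no stated SD for M, avoidable measurement noise is worth removing.

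A second issue lies beside the first. The Aim 2 definition treats infused glucose as equal to metabolized glucose. That needs a constant glucose level in the window, and neither range guarantees one.

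**Working it through.** The plan states no figure that depends on the glucose range, so there is none to reproduce. The check compares the texts and then does simple arithmetic on the two ranges.

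**Step 1. Do the statements cover the same procedure?** The Insulin entry refers to all participants in the clamp studies, monitored every 5 minutes. The Visit 1.2 procedure uses the same interval: "Plasma glucose is measured every 5 minutes, with concentrations determined immediately upon collection". The Intralipid entry that follows the Insulin entry is marked as applying to Aim 1A only; the Insulin entry has no such mark. The Aim 1A infusion text mentions clamp conditions but gives no range. Nothing therefore assigns 90-100 to Aim 1A, and the conflict reaches the Aim 2 clamp.

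**Step 2. Where do the ranges differ?**

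| | Visit 1.2 and Dextrose | Insulin |
|---|---|---|
| Lower limit (mg/dl) | 90 | 90 |
| Upper limit (mg/dl) | 110 | 100 |
| Width (mg/dl) | 110 − 90 = 20 | 100 − 90 = 10 |
| Midpoint (mg/dl) | (90 + 110)/2 = 100 | (90 + 100)/2 = 95 |

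The share of the wider range that lies outside the narrower one is (110 − 100)/20 = 0.5. Half of the wider band counts as euglycemic under two statements and not under the third.

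**Step 3. How much could the choice of range move M?** The documents do not say how glucose uptake at fixed insulin depends on the glucose level, so this is an assumption with a range.

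- Uptake independent of glucose within the band: shift 0%.
- Uptake proportional to glucose, with operators aiming at the midpoint of whichever range they follow: 100/95 − 1 = 5.3%.

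The difference attributable to the two ranges at their midpoints is therefore 0 to about 5% of M. It appears in a woman's paired difference only if one of her visits followed one range and the other visit followed the other.

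**Step 4. Drift in the final 30 minutes.** If all readings stay in range, glucose can still change by up to 20 mg/dl (wider range) or 10 mg/dl (narrower range) across the window, which is 20/30 = 0.67 or 10/30 = 0.33 mg/dl per minute. The glucose that accumulates in, or leaves, the body pool is

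(change in glucose / 30 min) × V,

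where V is the glucose distribution volume per kg of body weight. If glucose rises, infused glucose exceeds metabolized glucose by this amount; if it falls, the reverse holds. For each 1 dl/kg of V assumed, the maximum error is 0.33 or 0.67 mg/kg/min. The documents give neither V nor a typical M, so this cannot be turned into a percentage.

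The correction needs no new data. Sampling every 5 minutes gives 30/5 = 6 intervals in the window, enough to estimate the change.

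**The case against.** The strongest reply is that this is a drafting slip with little effect on the analysis. Several parts of it stand.

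- The ranges are nested. A clamp held at 90-100 mg/dl satisfies all three statements.
- Only the clamp procedure formally defines euglycemia. The other figure appears once, in a paragraph on hypoglycemia.
- Visit 6.2 repeats Visit 1.2, so a range applied consistently at both visits would largely cancel in the paired difference.
- No sample size or power figure depends on the range.

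A reader might infer something stronger: that a woman held near 95 mg/dl before the diet and 105 after it would show a change in M of 105/95 − 1 = 10.5% with no change in insulin sensitivity, and that the contradiction therefore biases the primary comparison. The documents do not support this. Both values lie within 90-110 alone, so the example would survive if every statement said 90-110. Under the same proportionality assumption, the narrower range alone permits 100/90 − 1 = 11%. These figures measure the width of a clamp band, not the effect of having two bands. Bias would also need a systematic change of range between visits, and nothing in the documents suggests one.

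A reader might also infer that staff have conflicting limits for hypoglycemia. They do not: the lower limit is 90 mg/dl in all three places.

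It can fairly be said that the drift correction is a separate matter, and would be just as arguable if the three ranges agreed. That is accepted, and it is presented here as separate. It does not make the correction unnecessary, because the Aim 2 definition declares the window steady and provides no adjustment when it is not.

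**Conclusion.** The inconsistency is real but limited to the upper limit, 110 against 100 mg/dl. It matters because it is an operating threshold for the Aim 2 primary measurement. Its expected effect is some avoidable noise in M, from 0 to about 5% at the midpoints. The upper figure rests on two assumptions outside the documents: proportional uptake, and operators who aim at midpoints. No bias between visits is shown. With no SD for M in the plan, the effect on the power of the paired comparison cannot be stated.

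The uncorrected drift in the final 30 minutes is a second, independent weakness. Its size depends on how far glucose actually moved and on the distribution volume assumed.

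Overall severity is minor. The point is worth acting on because the remedy costs so little.

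**What to change.** 1. Reconcile the Visit 1.2 procedure with the Insulin and Dextrose risk entries, so that one range is stated everywhere and used at both clamp visits. The sponsor must decide which.
2. In the Aim 2 analysis, correct M for the change in glucose over the final 30 minutes: subtract (change in glucose / 30 min) × V from the mean infusion rate per kg, with V stated in advance. Apply the same rule at both visits.
3. Optionally, report M divided by mean steady-state glucose as a sensitivity analysis, to show whether differences in the level held affect the result.

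The cost is a wording change and a short calculation on the 5-minute values already collected, with no new visits, blood or participants. It can still be done if the clamps are complete. The downside is that the drift correction brings in an assumed distribution volume, which should be reported alongside the uncorrected M.

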**Inclusion Criteria:**

- BMI at least 18 but less than 25 kg/m^2

**IRB #:** 15-1052  
**Project Title:** Reprometabolic Syndrome Mediates Subfertility in Obesity  
**Principal Investigator:** [name]

- No history of chronic disease affecting hormone production, metabolism or clearance
- No use of medications known to alter or interact with reproductive hormones or insulin metabolism (e.g. thiazolidinediones, metformin)
- No use of reproductive hormones within 3 months of enrollment
- Normal prolactin and thyroid stimulating hormone levels at screening
- History of regular menstrual cycles every 25-35 days
- Use of a reliable method of contraception (female or male partner sterilization; IUD; abstinence; diaphragm)
- Normal hemoglobin A1c
- Screening hemoglobin  $\geq 11\text{gm/dl}$

Exclusion criteria:

- Women with a baseline dietary assessment indicative of  $>40\%$  daily calorie consumption from fat (as calculated based upon initial 3 day diet record) will be excluded, as the impact of increasing their dietary fat intake may be minimal.
- Women with current or a history of diabetes, prediabetes, or gestational diabetes.
- Women with fasting triglycerides  $>300\text{mg/dl}$  at screening will be excluded, as they might be at risk for acute elevation of triglycerides and even pancreatitis if placed on a high fat diet.
- Inability to comply with the protocol. Individuals who travel frequently, or who eat most of their meals outside of their home will be excluded, as it will be difficult to impossible for them to comply with the diet, to pick up the food cartons, etc.
- Because high proportions of dairy fat will be needed to attain 48% calories from fat in the diet, vegans and lactose intolerant individuals will be excluded.
- Pregnant women or women planning to become pregnant will be excluded.

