Aim 1B will induce a chronic model of the reprometabolic syndrome by administering a eucaloric high fat diet for one month while monitoring gonadotropin pulsatility and daily urinary reproductive hormone excretion. In Aim 1b we want to demonstrate that a eucaloric high fat diet can induce insulin resistance and/or elements of the reprometabolic syndrome in women.

Aims 2 and 3 will be an exemption of analysis from the procedures performed and samples collected in Aims 1.A and 1.B. They will not require additional enrollment of study subjects or additional procedures.

**Pilot:** consisted of the Principle Investigator testing out the proposed diet intervention for Aim 1.B. The test diet was given for two weeks. There were no subjects consented or enrolled, and the Investigator declined compensation.

**Aim 1A:** will consist of four visits: a screening visit (12 hour fast required) and three study visits. During the screening visit participants will be provided with instructions and supplies to collect their daily morning urine and to use home ovulation predictor kits. Determining the day of ovulation will allow us to better predict the timing of the following menses (which almost always occurs 12-15 days after the urinary LH surge identified by the ovulation predictor kit). Accurate prediction of cycle Day 1 will permit more efficient scheduling of the frequent sampling studies, which must occur within a window of 1-4 days after the onset of menses (cycle days 2-5). We will ask participants to track their menstrual cycle by recording the day they start their period and the day that they ovulate and notify the study coordinator when evidence of a urinary LH surge has occurred. This will involve dipping a test stick in urine for several days to see if it changes color. Additional ovulation prediction kits will be provided if needed to the participants at the Visit 1 & 2. Participants will be administered saline only (limited subsample), saline + heparin infusion, and an insulin/intralipid/heparin infusion over 6 hours. Each participant will receive at least a saline+heparin infusion and an insulin/intralipid/heparin infusion, but

IRB #:

15-1052

Project Title:

Reprometabolic Syndrome Mediates Subfertility in Obesity

Principal Investigator: [name]

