the order in which the treatments are given will be randomly assigned. The insulin/intralipid/heparin infusion will consist of 20% lipid emulsion (45ml/h), heparin (24 units/kg/hr), and insulin (20 mU/m2/min) under euglycemic clamp conditions (maintained by using dextrose). Saline will be infused at a rate of 200 ml/h with heparin (24 units/kg/hr). During the saline only visit, heparin will not be infused. We have added a 'saline only' visit to validate the findings of the saline+heparin infusion study and to rule out any independent effect of heparin. At the same time, participants will undergo a 6-hour frequent blood sampling session at each visit. Muscle oxygenation will also be measured before and at 4 hours of both infusions. Partial thromboplastin time (PTT) levels will be followed with heparin infusion adjustments as needed to avoid over-anticoagulation. Each visit will be performed in the early follicular phase of the menstrual cycle and will be completed in consecutive cycles whenever possible, but no longer than within 4 cycles from the first study. Please see table description below:

	Pre-cycle 1	Visit 1	Visit 2	Visit 3
Visit#	L0=screen	L1	L2	L3
Description/Duration	2 hours	6 hours Concurrent FSS infusion*	6 hours Concurrent FSS infusion*	6 hours Concurrent FSS infusion*
Cycle Day		2-5	2-5	2-5
History	X			
Physical	X			
Pregnancy Test		X	X	X
Routine safety labs (CBC/CMP)	X	X	X	X
Hemoglobin A1C	X			
Prolactin	X			
Fasting Lipid Panel	X	X	X	X
TSH	X			
PTT	X	X	X	X
FFA	X	X	X	X
Informed Consent	X			
Weight	X	X	X	X
Ovulation Prediction Kits	X	X	X	
Frequent blood sampling		X	X	X
Administration of GnRH		X	X	X
Muscle Oxygen Measurement		X	X	X
Infusion*		X*	X*	X*

\*participants will receive either an insulin +lipid + heparin infusion, a heparin + saline (control), or saline only in random order

IRB #: 15-1052  
Project Title: Reprometabolic Syndrome Mediates Subfertility in Obesity  
Principal Investigator: [name]

**Aim 1B:** will consist of 11 in-person visits.

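### Aim 1A heparin is described as very low dose but starts at 1.33 times the protocol's own standard anticoagulation rate, and no written eligibility or pre-infusion rule covers bleeding risk, platelets, baseline PTT, prior heparin reaction or aspirin/ibuprofen use

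*Combined protocol and SAP*

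**What the plan says.** **Dose.** Under Study Design and Research Methods, the Aim 1A active infusion includes "heparin (24 units/kg/hr), and insulin (20 mU/m2/min) under euglycemic clamp conditions". The control visit has the same heparin rate: "Saline will be infused at a rate of 200 ml/h with heparin (24 units/kg/hr"). Infusions last 6 hours, and each woman has at least these two heparin visits.

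**How the dose is described.** The heparin paragraph under Risks of medications to be administered says "Heparin will be used at very low doses in this experiment and may induce short term anticoagulation". It goes on to use the low dose as the reason for not expecting thrombocytopenia or osteopenia. The same paragraph names hemorrhage, thrombocytopenia and anaphylactic reactions as known adverse reactions to heparin.

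**Monitoring.** The numbered items in that section state: "aPTT will be measured during peak infusion (mid-interval) at ~3 hours". They continue: "The heparin infusion rate will be reduced by 50% if aPTT is > 100, and by 25% (to standard anticoagulation dosing") when the aPTT is 80-100. A further aPTT follows at 6 hours, and discharge is tied to an aPTT below 120 seconds.

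**Timing.** Visits are tied to the "frequent sampling studies, which must occur within a window of 1-4 days after the onset of menses (cycle days 2-5").

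**Who may be infused.** The medication criterion reads "No use of medications known to alter or interact with reproductive hormones or insulin metabolism (e.g. thiazolidinediones, metformin"). The only blood-count limit is a hemoglobin of at least 11 g/dl. The Aim 1A visit table schedules CBC/CMP and PTT at screening and at all three visits, with no limit attached to platelets or PTT. History and physical are marked at screening only. The one rule on antiplatelet drugs is "Aspirin and Ibuprofen should be avoided for at least 2 hours if the patient is discharged with an abnormal aPTT (>35 seconds").

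**The concern.** Two parts of the plan do not fit together. The risk section calls the dose very low, while the rate-adjustment rule treats the starting rate as higher than standard anticoagulation. Anyone who judges participant risk from the risk section alone gets the wrong picture of the dose, and the thrombocytopenia statement rests on a reason that the dosing contradicts.

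Separately, the protections that apply once heparin is running are specific, but those that decide who may start are not. Taken literally, the written criteria admit a volunteer with a known bleeding disorder, a low platelet count, an earlier heparin reaction, or aspirin or ibuprofen taken that morning. An aPTT measures the anticoagulant response. It does not measure platelet count, drug-impaired platelet function or allergy, so later aPTT checks do not fill that gap. The volunteers are normal-weight women in a mechanistic study with no treatment benefit described, which raises the standard for written selection rules.

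**Working it through.** **1. Implied standard rate.** The protocol gives no figure in units/kg/hr for standard anticoagulation, so it has to be derived from two inputs.

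- Starting rate (Study Design and Research Methods, Aim 1A): 24 units/kg/hr at both heparin visits.
- Cut that reaches standard dosing (Risks of medications to be administered, heparin item 2): 25%.

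Standard = 24 × (1 − 0.25) = 18 units/kg/hr. Start relative to standard = 24 / 18 = 1.33, or 33% above. The larger cut gives 24 × 0.5 = 12 units/kg/hr. The first in-infusion check is the mid-interval one, so the cut is taken from the starting rate.

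**2. Exposure before the first in-infusion aPTT.** Formula: rate × time. The protocol says about 3 hours; I take 2.5 to 3.5 hours as the range.

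| Time of first aPTT | At 24 units/kg/hr | At 18 units/kg/hr |
|---|---|---|
| 2.5 h | 60 units/kg | 45 units/kg |
| 3 h | 72 units/kg | 54 units/kg |
| 3.5 h | 84 units/kg | 63 units/kg |

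A full 6-hour visit with no cut gives 24 × 6 = 144 units/kg, against 18 × 6 = 108.

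**3. Number of infusions.** 12 women (Study procedures) × 2 heparin visits = 24 infusions. With the 10 women named in the Data Analysis Plan, 10 × 2 = 20.

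**4. Eligibility criteria.** The list has 9 inclusion and 6 exclusion criteria, 15 in all. None concerns a bleeding disorder, platelets, a clotting test, an earlier heparin reaction, or anticoagulant or antiplatelet drugs. The chronic-disease criterion is confined to hormone production, metabolism or clearance. The list does contain an intervention-specific safety exclusion: fasting triglycerides above 300 mg/dl, because of the high-fat diet. Heparin has no counterpart. Several of the 15 concern diet, so the count shows absence only and is not a rate.

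**5. Day-of-visit rules.** Before each frequent sampling study the protocol requires the menstrual history to be verified and a pregnancy test. It does not require a question about aspirin, ibuprofen or bleeding. CBC and PTT are scheduled at each visit, but no result has to be seen, or fall within a limit, before heparin starts.

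**The case against.** The strongest reply is that the protocol does not handle heparin as a trivial exposure.

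- The exact rate is stated, and the sentence with the low-dose label also admits short-term anticoagulation.
- Rate cuts and a discharge limit are specified.
- Heparin is given only where nurses monitor continuously and epinephrine is at hand, which protects against an allergic reaction from the first minute.
- The Consent/Screening Process section describes the screening laboratory tests as qualifying, and PTT is among the Aim 1A screening tests.
- The Data and Safety Monitoring Plan has the safety officer review the protocol and the termination guidelines before enrollment.
- A careful investigator would probably turn away a volunteer with a known bleeding disorder.
- Consent pages are not in the public copy, so pre-visit drug instructions may exist there.

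All of this stands, and it limits the point to missing written criteria and action limits; testing and monitoring are not absent. It does not close the gap. A qualifying test with no stated limit leaves the decision to unstated judgement. Nursing and epinephrine address allergy but not platelet count or a drug taken that morning. Instructions in a consent form would not be an eligibility or go/no-go rule in the protocol.

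A reader might also take the CBC described under Risks of frequent blood sampling, whose stated purpose is to detect anemia, as proof that the Aim 1A CBCs are not meant for platelets. That does not follow. That CBC is taken at the end of the pulsatility study, and the text does not say why the routine safety labs are drawn. It may even supply a platelet count after the first infusion.

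**Conclusion.** The point holds in two parts. First, the low-dose description is wrong on the protocol's own terms: the start is 1.33 times its standard rate, so the thrombocytopenia statement needs a different basis. Second, no written eligibility or pre-infusion rule covers the bleeding-related items listed above, and the single aspirin/ibuprofen rule starts only after discharge. Followed exactly, the plan lets a woman who took either drug that morning start an above-standard infusion, with the first scheduled in-infusion aPTT at about 3 hours. This should be fixed.

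The ratio rests only on the stated rate and the stated cut. The dose totals assume a constant rate and no bolus, and none is described.

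Some stronger readings are tempting but not supported:

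- **That serious bleeding or thrombocytopenia is likely.** The documents give no event rate and no number of volunteers affected. The 72 and 144 units/kg and the 20 to 24 infusions describe exposure, not harm.
- **That the dose should come down or the monitoring is inadequate.** Nothing here shows either.
- **That criteria were left out because the dose was thought low.** The protocol gives no reason for the omission.
- **That every infusion takes place during menstrual bleeding.** Cycle days 2-5 mean during or just after menses.

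**What to change.** 1. **Risk wording.** In the heparin paragraph, replace the low-dose wording with the actual rate: 24 units/kg/hr for up to 6 hours at both heparin visits, above standard anticoagulation dosing. Base any thrombocytopenia statement on brief exposure.
2. **Aim 1A exclusions.** Add known bleeding disorder; earlier heparin-induced thrombocytopenia or heparin hypersensitivity; current anticoagulant or antiplatelet use; and screening platelet count or PTT outside the laboratory's reference range.
3. **Check before each heparin infusion.** Confirm no aspirin or ibuprofen within a washout set by the principal investigator and safety officers. Compare the latest platelet count and PTT with a stated go/no-go limit. At the second heparin visit, use a platelet count taken after the first.
4. **Advice to participants.** Extend the aspirin/ibuprofen advice to the time before and during the infusion.

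The heparin rate, aPTT checks, rate cuts, discharge limit and counseling stay as they are.

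**Cost.** A short amendment. History, CBC and PTT are already collected, so no new type of test is needed, but a platelet result must be available before heparin starts. A few volunteers may be excluded. A woman who has taken ibuprofen may miss the cycle-day window and wait one cycle (25-35 days), which the limit of 4 cycles from the first study can usually absorb.
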